2.4 Correlative Studies Background

2.4.1 MYD88 L265P and CXCR4-WHIM-like mutations, and FcγRIIIA-158 (CD16) polymorphisms

One of the major advances in the field of WM has been the recent discovery of a recurrent genetic abnormality, the MYD88 L265P mutation (Treon 2012). Sanger sequencing detected such mutation in tumor samples from 49 out of 54 patients (91%) with WM. Interestingly, the mutation was not detected in normal cells from WM patients and B-cells from healthy donors, and was absent or rarely expressed in cells from patients with multiple myeloma or marginal zone lymphoma. Such finding has been independently validated in subsequent studies from Italy, France the United States with prevalence rates ranging between 90-100% (Varettoni 2013; Poulain 2013; Ondrejka 2013). More recently, allele-specific PCR assays have been developed to improve the sensitivity of detection of the mutation and the quantification of the MYD88 L265P mutation burden (Xu 2013).

More recently, mutations in the CXC chemokine receptor 4 (CXCR4) gene were identified in 16 out of 55 (29%) WM patients investigated (Cao 2012). CXCR4 mutations are the second most common mutations found in WM patients. Such mutations are similar to the ones seen in patients with WHIM syndrome, an autosomal dominant genetic disorder characterized by warts, hypogammaglobulinemia, infections and myelokathexis (Hunter 2013) conferring gain of function and decreased CXCR4 internalization. In preclinical and clinical studies, CXCR4-WHIM mutations have been associated with lower responses to Bruton tyrosine kinase inhibitors (Cao 2013), but their significance in proteasome inhibitor-treated patients is not yet known.

As part of these efforts, the impact of FcγRIIIA-158 (CD16) polymorphisms as a predictor of categorical response in WM will be assessed. In previous studies by Treon et al, the presence of at least one valine at amino acid position 158 at FcγRIIIA (CD16) predicted for response to rituximab (Treon 2005b). Patients displaying either valine/valine (V/V) or valine/phenylalanine (V/F) had a four-fold higher rate of response to single agent rituximab compared to patients displaying phenylalanine/phenylalanine (F/F) alone at FcγRIIIA-158. The impact of polymorphisms at FcγRIIIA-158 on response outcome has also been validated in other indolent

CONFIDENTIAL

This document is confidential. Do not disclose or use except as authorized.

lymphomas (Cartron 2002; Weng 2003), and has lead to U.S. FDA clearance for such testing. The impact of FcγRIIIA-158 polymorphisms in predicting categorical response attainment in WM patients has recently been reported. Hunter et al demonstrated that better categorical responses (i.e. VGPR or better) were associated with V/V or V/F at FcγRIIIA-158 in patients who received combination therapy with rituximab (Treon 2011). As such, as part of these studies we will seek to determine the impact of FcγRIIIA-158 polymorphisms on categorical response attainment in WM patients in this study.

3.PARTICIPANT SELECTION

3.1Eligibility Criteria

Participants must meet the following criteria on screening examination to be eligible to participate in the study:

Each patient must meet all of the following inclusion criteria to be enrolled in the study:

1. Male or female patients 18 years or older.
2. Voluntary written consent must be given before performance of any study related procedure not part of standard medical care, with the understanding that the patient may withdraw consent at any time without prejudice to future medical care.
3. Female patients who:
 - Are postmenopausal for at least 1 year before the screening visit, OR
 - Are surgically sterile, OR
 - Are of childbearing potential,
 - agree to practice 2 effective methods of contraception, at the same time, from the time of signing the informed consent form through 90 days after the last dose of study drug, OR
 - Agree to practice true abstinence when this is in line with the preferred and usual lifestyle of the subject. (Periodic abstinence [eg, calendar, ovulation, symptothermal, post-ovulation methods] and withdrawal are not acceptable methods of contraception.)

Male patients, even if surgically sterilized (ie, status post-vasectomy), must agree to one of the following:

- Agree to practice effective barrier contraception during the entire study treatment period and through *90 days* after the last dose of study drug, OR
 - Agree to practice true abstinence when this is in line with the preferred and usual lifestyle of the subject. (Periodic abstinence (eg, calendar, ovulation, symptothermal, post-ovulation methods] and withdrawal are not acceptable methods of contraception.)
4. Patients must have a clinicopathological diagnosis of WM (Owen 2003), with symptomatic disease meeting criteria for treatment using consensus panel criteria from the Second International Workshop on WM (Kyle 2003) or serum IgM >6000 mg/dL, and measurable disease, defined as presence of immunoglobulin M (IgM) paraprotein with a minimum IgM level of >2 times the upper limit of normal.
 5. Eastern Cooperative Oncology Group (ECOG) performance status of 0, 1, or 2.

CONFIDENTIAL

This document is confidential. Do not disclose or use except as authorized.

6. Patients must meet the following clinical laboratory criteria
7. Absolute neutrophil count (ANC) $\geq 1,000/\text{mm}^3$ and platelet count $\geq 75,000/\text{mm}^3$. Platelet transfusions to help patients meet eligibility criteria are not allowed within 3 days before study enrollment.
8. Total bilirubin $\leq 1.5 \times$ the upper limit of the normal range (ULN).
9. Alanine aminotransferase (ALT) and aspartate aminotransferase (AST) $\leq 3 \times$ ULN.
10. Calculated creatinine clearance ≥ 30 mL/min.

3.2 Exclusion Criteria

Patients meeting any of the following exclusion criteria are not to be *enrolled in the study*:

1. Female patients who are lactating or have a positive serum pregnancy test during the screening period.
2. Major surgery within 14 days before enrollment.
3. Central nervous system involvement.
4. Infection requiring systemic antibiotic therapy or other serious infection within 14 days before study enrollment.
5. Evidence of current uncontrolled cardiovascular conditions, including uncontrolled hypertension, uncontrolled cardiac arrhythmias, symptomatic congestive heart failure, unstable angina, or myocardial infarction within the past 6 months.
6. Systemic treatment, within 14 days before the first dose of MLN9708, with strong inhibitors of CYP1A2 (fluvoxamine, enoxacin, ciprofloxacin), strong inhibitors of CYP3A (clarithromycin, telithromycin, itraconazole, voriconazole, ketoconazole, nefazodone, posaconazole) or strong CYP3A inducers (rifampin, rifapentine, rifabutin, carbamazepine, phenytoin, phenobarbital), or use of Ginkgo biloba or St. John's wort.
7. Known hepatitis B or C virus, or human immunodeficiency virus (HIV) infection.
8. Any serious medical or psychiatric illness that could, in the investigator's opinion, potentially interfere with the completion of treatment according to this protocol.
9. Known allergy to any of the study medications, their analogues, or excipients in the various formulations of any agent.
10. Known GI disease or GI procedure that could interfere with the oral absorption or tolerance of ixazomib including difficulty swallowing.
11. Diagnosed or treated for another malignancy within 2 years before study enrollment or previously diagnosed with another malignancy and have any evidence of residual disease. Patients with non-melanoma skin cancer or carcinoma in situ of any type are not excluded if they have undergone complete resection. Male patients with incidental histological findings of prostate cancer (T1a or T1b using the TNM (tumor nodes, metastasis) clinical staging system are not excluded.
12. Participation in other clinical trials, including those with other investigational agents not included in this trial, within 30 days of the start of this trial and throughout the duration of this trial.

4. REGISTRATION PROCEDURES

4.1 General Guidelines for DF/HCC and DF/PCC Institutions

CONFIDENTIAL

This document is confidential. Do not disclose or use except as authorized.

Institutions will register eligible participants in the Clinical Trials Management System (CTMS) OnCore. Registration must occur prior to the initiation of therapy. Any participant not registered to the protocol before treatment begins will be considered ineligible and registration will be denied.

An investigator will confirm eligibility criteria and complete the protocol-specific eligibility checklist.

Following registration, participants may begin protocol treatment. Issues that would cause treatment delays should be discussed with the Principal Investigator. If a participant does not receive protocol therapy following registration, the participant’s registration on the study must be canceled. Registration cancellations must be made in OnCore as soon as possible.

4.2 Registration Process for DF/HCC and DF/PCC Institutions

5. TREATMENT PLAN

Treatment will be administered on an outpatient or inpatient basis. Expected toxicities and potential risks as well as dose modifications for ixazomib, rituximab, and dexamethasone are described in Section 6 (Expected Toxicities and Dosing Delays/Dose Modification). No investigational or commercial agents or therapies other than those described below may be administered with the intent to treat the participant’s malignancy.

IDR Induction Phase					
Agent	Premedications	Dose	Route	Schedule	Cycle Length
Dexamethasone	None	20 mg	IV or PO	Days 1, 8, 15 Before ixazomib and rituximab	Every 4 weeks for Cycles 1-6 Rituximab omitted from cycles 1 and 2
Ixazomib	None	4 mg	PO	Days 1, 8 15 After dexamethasone	
Rituximab	Diphenhydramine 25-50 mg PO/IV Acetaminophen 650-1000 mg PO Famotidine 20mg IV	375 mg/m ²	IV infusion	Day 1 After Ixazomib	

IDR Maintenance Phase					
Agent	Premedications	Dose	Route	Schedule	Cycle Length

CONFIDENTIAL

This document is confidential. Do not disclose or use except as authorized.

Dexamethasone	None	20 mg	IV or PO	Day 1, 8, and 15 Before Ixazomib and Rituximab	Every 8 weeks +/- 2 weeks for Cycles 1-6
Ixazomib	None	4 mg	PO	Day 1, 8, and 15 After Dexamethasone	
Rituximab	Diphenhydramine 25-50 mg PO/IV Acetaminophen 650-1000 mg PO Famotidine 20mg IV	375 mg/m ²	IV infusion	Day 1 After Ixazomib	

5.1 Pre-Medication

5.1.1 Rituximab

To prevent infusion related or hypersensitivity reactions from occurring during infusion of rituximab, premedication consisting of diphenhydramine 25-50 mg PO/IV, and Acetaminophen 650-1000 mg PO should be given to patients prior to administration of all infusions of rituximab, unless the patient has an allergy to either medication. Since transient hypotension may occur during rituximab administration, consideration should be given to withholding anti-hypertensive medications 12 hours prior to rituximab infusion. Prophylactic anti-emetic therapy for rituximab is generally not necessary, but may be used at the discretion of the treating physician.

5.2 Agent Administration

5.2.1 Ixazomib

5.2.1.1 Form of Ixazomib

All later phase studies are conducted with the Capsule formulation.

Ixazomib Capsules

The ixazomib drug product is provided in strengths of 4.0-, 3.0-, and 2.3-mg and 2.0-, 0.5-, and 0.2 mg capsules as the active boronic acid. The different dose strengths are differentiated by both capsule size and color as described below:

Dose Strength	Capsule Size	Capsule Color
4.0 mg	Size 4	Ivory
3.0 mg	Size 3	Light gray
2.3 mg	Size 2	Light pink
2.0 mg	Size 2	Swedish orange
0.5 mg	Size 3	Dark green
0.2 mg	Size 4	White opaque

CONFIDENTIAL

This document is confidential. Do not disclose or use except as authorized.

Ixazomib Capsules are individually packaged in foil-foil blisters with a paper backing for child resistance.

For additional details, please see the ixazomib IB.

5.2.1.2 Hydration

IV hydration is recommended prior to ixazomib for Cycle 1 of induction therapy ONLY. This will consist of 500 mL normal saline or other appropriate IV fluid over 1 hour. IV hydration in subsequent cycles will be at the discretion of the Principal Investigator.

5.2.1.3 Ixazomib Administration

Ixazomib should be administered after dexamethasone each and every cycle, unless dexamethasone is omitted. Please refer to section 2.1.3.3. The order of administration should be dexamethasone followed by ixazomib followed by rituximab.

All protocol-specific criteria for administration of study drug must be met and documented before drug administration. Study drug will be administered or dispensed only to eligible patients under the supervision of the investigator or identified sub-investigator(s). Patients should be monitored for toxicity, as necessary, and doses of **ixazomib** should be modified as needed to accommodate patient tolerance to treatment; this may include symptomatic treatment, dose interruptions, and adjustments of **ixazomib** dose (see Section 6.2).

Capsules of **ixazomib** will also be referred to as study drug. Study drug will be supplied by Millennium as capsules of 2.3, 3.0 and 4.0 mg **ixazomib**. The prescribed administration of **ixazomib** doses in this study is 4 mg **ixazomib** PO once weekly (+/-3 days) on days 1, 8 and 15 in a 28-day cycle during induction therapy, and once on days 1, 8, and 15 in each maintenance cycle.

Patients should be instructed to swallow **ixazomib** capsules whole, with water, and not to break, chew, or open the capsules. Study drug should be taken on an empty stomach (no food or drink) at least 1 hour before or 2 hours after a meal. Each capsule should be swallowed separately with a sip of water. A total of approximately 8 ounces (240 mL) of water should be taken with the capsules.

Missed doses can be taken as soon as the patient remembers if the next scheduled dose is 72 hours or more away. A double dose should not be taken to make up for a missed dose. If the patient vomits after taking a dose, the patient should not repeat the dose but should resume dosing at the time of the next scheduled dose.

Ixazomib drug product is an anti-cancer drug. Refer to the published institutional guidelines regarding the proper handling and disposal of anti-cancer agents.

Investigational **ixazomib** (expired or end of study) should be destroyed on site according to the institution's standard operating procedure. Be sure to document removal and destruction on drug

CONFIDENTIAL

This document is confidential. Do not disclose or use except as authorized.

accountability logs.

5.2.2 Rituximab

5.2.2.1 Form of Rituximab

Rituximab is supplied as a sterile, colorless, preservative free liquid concentrate for intravenous (IV) administration. Rituximab is supplied at a concentration of 10 mg/ml in either 100 mg (10 mL) or 500 mg (50 mL) single-use vials. The product is formulated for IV administration in 9 mg/ml sodium chloride, 7.35-mg/mL sodium citrate dehydrate, 0.7 mg/mL polysorbate 80, and sterile water for injection. The pH is adjusted to 6.5.

5.2.2.2 Method of Procurement for Rituximab

Rituximab is a commercially available drug, which is approved by the U.S. Food and Drug Administration for use in patients with low grade and follicular Non-Hodgkin Lymphoma (NHL). Use of this drug to treat patients with lymphoplasmacytic lymphoma (Waldenstrom's macroglobulinemia) is considered to be a labeled indication since it is included under the indolent NHL indication. Drug used in this study will be billed to patient and/or their third party payer (insurance).

5.2.2.3 Drug Stability and Compatibility of Rituximab

Rituximab vials are stable at 2°-8° C. Vials of rituximab beyond expiration date on the carton should not be used. Rituximab vials should be protected from direct sunlight.

5.2.2.4 Preparation of Rituximab

Rituximab is diluted to a final concentration of 1 to 4 mg/ml into an infusion bag containing either 0.9% sodium chloride USP or 5% dextrose in water USP. Rituximab solutions for infusion are stable at 2° to 8° C for 24 hours and at room temperature for an additional 12 hours. No incompatibilities between rituximab and polyvinylchloride or polyethylene bags have been reported.

5.2.2.5 Rituximab Pre-Treatment Medications

To prevent infusion related or hypersensitivity reactions from occurring during infusion of rituximab, premedication consisting of diphenhydramine 25-50 mg IV, and acetaminophen 650-1000 mg PO should be given to patients prior to administration of all infusions of rituximab, unless the patient has an allergy to either medication. Lower doses may be used if the patient demonstrates tolerance. Since transient hypotension may occur during rituximab administration, consideration should be given to withholding anti-hypertensive medications 12 hours prior to rituximab infusion. Prophylactic anti-emetic therapy for rituximab is generally not necessary, but may be used at the discretion of the treating physician.

5.2.2.6 Rituximab Treatment Schedule and Administration

CONFIDENTIAL

This document is confidential. Do not disclose or use except as authorized.

Rituximab should be administered after ixazomib on day 1 of induction cycles 3-6 and maintenance cycles 1-6. The order of administration should be dexamethasone followed by ixazomib followed by rituximab. Please see section 5.2.1.3.

During the induction phase Cycles 3-6 on Day 1 and the maintenance phase Cycles 1-6 on Day 1, Rituximab 375 mg/m² IV is to be administered at an initial rate of 50 mg/hour for the first hour then escalate the rate in 50 mg/ hours increments approximately every 30 minutes, to a maximum of 400 mg/hour. If hypersensitivity or an infusion-related event develops such as T>101.3, mucosal edema, or a >30mm Hg decrease in SBP, interrupt the infusion, administer hypersensitivity rescue medications. When symptoms have resolved, the infusion can continue at one-half the previous rate and escalate in 50 mg/hr increments approximately each half hour, as tolerated. The infusion may be discontinued early at the discretion of the treating investigator. For patients who have tolerated previous infusions without hypersensitivity, subsequent infusions can be administered at an initial rate of 100 mg/hr, and increased by 100 mg/hr increments at approximately 30-minute intervals, to a maximum of 400 mg/hr as tolerated. Alternatively, subsequent infusions can be administered at an initial rate of 20 percent of the total dose over 30 minutes, followed by the remaining 80 percent of the total dose over 60 minutes.

Vital signs: At the first infusion, vital signs should be checked and recorded at baseline, at the first rate change (usually at the approximately 1 hour point), as needed for signs and symptoms of hypersensitivity reaction, and at the end of the infusion. For subsequent infusions, vitals should be taken at baseline, and as needed for signs or symptoms of a reaction.

5.2.2.7 First Infusion of Rituximab

The rituximab solution for infusion should be administered intravenously at an initial rate of 50 mg/hr. Rituximab should not be mixed or diluted with other drugs. If hypersensitivity or infusion related events do not occur, the infusion can be escalated in 50 mg/hr increments approximately every 30 minutes, to a maximum of 400 mg/hr. If hypersensitivity or an infusion-related event develops, such as, T>101.3, mucosal edema, or a >30mm Hg decrease in SBP interrupt the infusion, administer hypersensitivity rescue medications. When symptoms have resolved, the infusion can continue at one-half the previous rate and escalate in 50 mg/hr increments each half hour, as tolerated.

5.2.2.8 Subsequent Rituximab infusions

Subsequent rituximab infusions can be administered at an initial rate of 100 mg/hr, and increased by 100 mg/hr increments at approximately 30-minute intervals, to a maximum of 400 mg/hr as tolerated. Rituximab is administered intravenously. Alternatively, subsequent infusions can be administered at an initial rate of 20 percent of the total dose over 30 minutes, followed by the remaining 80 percent of the total dose over 60 minutes. To prevent infusion related or hypersensitivity events, **Rituximab is not to be administered as an intravenous push or bolus.**

5.2.2.9 Modification of Rate for Infusion of Rituximab

CONFIDENTIAL

This document is confidential. Do not disclose or use except as authorized.

In the event that patients develop an infusion related or hypersensitivity reaction to rituximab then the rate of drug administration is altered as described above. The total dose administered remains the same in such cases. In the event of serious or life threatening reactions, the infusion should be terminated and such adverse events reported. In the event of serious or life threatening events attributed to rituximab, patients may permanently discontinue rituximab and remain on the study after consultation with the overall PI.

5.2.3 Dexamethasone

5.2.3.1 Intravenous Dexamethasone

Each mL of clear, colorless sterile solution contains: dexamethasone sodium phosphate equivalent to dexamethasone phosphate 4 mg (equal to 3.33 mg of dexamethasone or roughly about 100 mg of hydrocortisone). Non-medicinal ingredients: creatinine, sodium citrate, sodium hydroxide (to adjust pH) and water for injection with sodium bisulfite, methylparaben, and propylparaben are added as preservatives. Store below 25°C. Do not freeze. Protect from light.

5.2.3.2 Contraindications and Drug interactions for Dexamethasone therapy

Refer to sections 2.1.3.3 and 2.1.3.4 for contra-indications and drug interactions with dexamethasone.

5.2.3.3 Dexamethasone Administration

Dexamethasone should be administered before ixazomib unless dexamethasone is omitted. Please refer to section 2.3.3.3. The order of administration should be dexamethasone followed by ixazomib followed by rituximab. Please see section 5.2.1.3.

During the induction phase, Cycles 1-6, Days 1, 8 and 15, a total of 20 mg IV or PO dexamethasone will be administered before ixazomib. During the maintenance phase, Cycles 1-8, Day 1, a total of 20 mg IV or PO dexamethasone will be administered.

20 mg oral dexamethasone may be substituted in the event of a drug supply shortage of IV dexamethasone and on days 8 and 15 of induction and maintenance for dosing outside of clinic. Administration method will be documented.

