1. OBJECTIVES

1.1 Study Design

This is a single-arm, open-label, prospective phase II study to evaluate the safety and efficacy of IDR in symptomatic untreated WM patients. The study treatment will consist on an induction and a maintenance phase. Dose modification will be permitted for toxicity.

IDR Induction:

Cycles 1 and 2 will consist on ixazomib 4 mg and dexamethasone 20 mg IV or PO administered on days 1, 8 and 15.

Cycles 3-6 will consist on ixazomib 4 mg PO and dexamethasone 20 mg IV or PO on days 1, 8 and 15, and rituximab 375 mg/m² IV on day 1 every 28 days.

Total duration of induction: 24 weeks.

IDR Maintenance:

Maintenance therapy will start 2 months ± 2 weeks after day 1 of cycle 6 and will consist on ixazomib 4 mg PO and dexamethasone 20 mg IV or PO administered on days 1, 8 and 15, and and rituximab 375 mg/m² IV administered on day 1 every 2 months for 1 year (6 cycles).

Total duration of maintenance: 52 weeks.

Supportive therapy:

Acyclovir 400 mg PO BID or Valacyclovir 1000mg PO QD will start on day 1 of study and will continue for 6 months after the last dose of ixazomib.

Famotidine 20 mg PO (or other gastritis prophylactic medication) will start on day 1 of study and will continue until the last dose of dexamethasone.

Acetaminophen 650 mg PO, diphenhydramine 50 mg PO and famotidine 20mg IV will be administered at least 30 minutes prior to each rituximab infusion.

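### Section 5.2.3.3 gives maintenance dexamethasone on Day 1 of eight cycles; the rest of the protocol gives days 1, 8 and 15 of six cycles (8 doses against 18)

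*Combined protocol and SAP*

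**What the plan says.** The administration section for dexamethasone (5.2.3.3) says: "During the maintenance phase, Cycles 1-8, Day 1, a total of 20 mg IV or PO dexamethasone will be administered". Its next paragraph allows oral dexamethasone "on days 8 and 15 of induction and maintenance for dosing outside of clinic", and Section 7.3.5 repeats that provision.

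Elsewhere the maintenance schedule is different:

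- Section 1.1 gives "dexamethasone 20 mg IV or PO administered on days 1, 8 and 15, and and rituximab", with maintenance running "every 2 months for 1 year (6 cycles", and states a total maintenance duration of 52 weeks.
- The maintenance table in Section 5 has, in the dexamethasone row, "Day 1, 8, and 15 Before Ixazomib and Rituximab", and for the cycle length "Every 8 weeks +/- 2 weeks for Cycles 1-6".
- Section 5.2.1.3 gives ixazomib after dexamethasone, "and once on days 1, 8, and 15 in each maintenance cycle".
- Section 5.2.2.6 gives the cycle count for the third drug: "Rituximab should be administered after ixazomib on day 1 of induction cycles 3-6 and maintenance cycles 1-6".
- Section 5.4 plans six induction and six maintenance cycles.
- The Section 9 calendar shows maintenance cycles 1 to 6 and marks dexamethasone on D1, D8 and D15.

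**The concern.** The sentence in 5.2.3.3 is current, operative text in the section that tells sites how to give this drug. It differs from the treatment table in two separate respects: eight cycles instead of six, and Day 1 instead of days 1, 8 and 15. The protocol does not say which text governs when two sections conflict.

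A site that worked from this sentence alone would omit dexamethasone before the day 8 and day 15 ixazomib doses throughout maintenance. That would change one component of a three-drug regimen whose toxicity profile is a primary objective (Section 1.2). The sentence also makes it unclear whether a missing day 8 or day 15 dose is a protocol deviation. That matters for the listing of major deviations in Section 14.3 and, possibly, for the Per-Protocol Set in Section 14.2.

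**Working it through.** The protocol prints no dose total for dexamethasone, so there is no stated figure to reproduce. The totals follow from the schedules.

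**Inputs.** Dose 20 mg (all sections). Induction: cycles 1 to 6, days 1, 8 and 15 (Sections 1.1, 5 and 5.2.3.3, which agree). Maintenance, reference schedule: cycles 1 to 6, days 1, 8 and 15 (Section 1.1, Section 5 table, Section 9). Maintenance, disputed sentence: cycles 1 to 8, Day 1 (Section 5.2.3.3). Maintenance cycle length: 8 weeks (Section 5 table).

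**Formulas.** Doses = cycles × dosing days per cycle. Total mg = doses × 20. Nominal length = cycles × 8 weeks. Shortfall = 1 − (doses under the reading ÷ reference doses).

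**Induction.** 6 × 3 = 18 doses = 360 mg, the same under every reading.

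| Reading of maintenance | Doses | mg | Shortfall in maintenance | Induction + maintenance | Shortfall overall | Nominal length |
|---|---|---|---|---|---|---|
| Reference: days 1, 8, 15 of cycles 1–6 | 6 × 3 = 18 | 360 | – | 36 doses, 720 mg | – | 48 weeks |
| A: Day 1 of cycles 1–8, literal | 8 × 1 = 8 | 160 | 1 − 8/18 = 56% | 26 doses, 520 mg | 1 − 26/36 = 28% | 64 weeks |
| B: Day 1 only, stopping at cycle 6 | 6 × 1 = 6 | 120 | 1 − 6/18 = 67% | 24 doses, 480 mg | 1 − 24/36 = 33% | 48 weeks |

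**Ixazomib doses left without dexamethasone.** Maintenance ixazomib is 6 × 3 = 18 doses. Under A and B the uncovered doses are days 8 and 15 of six cycles: 2 × 6 = 12 of 18, or 67%.

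**Which version is intended.** The two elements can be checked separately.

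- *Cycle count.* Section 1.1, the Section 5 table, Section 5.2.2.6, Section 5.4 and the Section 9 calendar all give six; no other section gives eight. Eight 8-week cycles would take 64 weeks against the stated 52. Six take 48 weeks, which fits a plan of about one year.
- *Dosing days.* Section 1.1, the Section 5 table and the calendar give days 1, 8 and 15. The oral-substitution provision in 5.2.3.3 and 7.3.5 has no meaning in maintenance unless dexamethasone is due on days 8 and 15. No other section limits maintenance dexamethasone to Day 1.

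Both elements of the disputed sentence are therefore wrong, and the documents settle what should replace them.

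**The case against.** The strongest reply is that the protocol corrects itself. Section 5.2.3.3 opens by placing dexamethasone before ixazomib, and its last paragraph assumes days 8 and 15 in maintenance. Section 5.2.1.3, the treatment table, the calendar and Section 7.3.5 all point the same way. A site would have to read one sentence in isolation to go wrong, and that sentence does not say Day 1 *only*. Reading A is also unrealistic, because no other section provides any treatment in maintenance cycles 7 and 8.

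Much of this stands. The practical risk is limited, and the percentages describe what each reading implies rather than what is likely to have happened. Two further limits also stand. The 18- and 36-dose references are planned maxima, since Sections 2.1.3.3 and 7.3.6 require dexamethasone to be omitted in several clinical circumstances, and those omissions are not deviations. Section 5.4 describes six cycles as the planned course that treatment may follow, although no other number of maintenance cycles has support.

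The reply does not remove the conflict. The other sections show which schedule is meant, but the section devoted to giving the drug still carries an instruction that, if followed, changes the treatment. Two independent elements are wrong, so this is more than one mistyped digit.

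**Conclusion.** The concern holds: the sentence is wrong as written and should be corrected. Against a reference of 18 maintenance doses (360 mg), it gives 8 (160 mg), or 6 (120 mg) if treatment ends at cycle 6. These figures assume full treatment with no delays, dose omissions or early stopping.

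The statistical consequences are small:

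- The primary analysis, alpha and power do not depend on this sentence.
- Full Analysis Set membership (Section 14.2) rests on measurable disease, one cycle of therapy and re-evaluation, so maintenance dexamethasone does not determine it.
- The exposure summaries in Section 14.5 report what was actually taken, so the sentence alone changes no output.
- Section 14.2 does not define a major deviation or tie it to dexamethasone counts. The classification of omissions could be blurred, but no effect on the Per-Protocol Set is shown.
- The documents do not show that any patient was mis-dosed.

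The case for correction rests on this being a contradictory dosing instruction for a study drug with a clear and nearly free remedy.

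**What to change.** Rewrite the maintenance sentence in Section 5.2.3.3 to specify dexamethasone 20 mg, IV or PO, before ixazomib on days 1, 8 and 15 of maintenance cycles 1 to 6. That agrees with Section 1.1, the Section 5 table, the calendar and Section 7.3.5, so no new clinical decision is needed.

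Use the same schedule as the reference when judging dexamethasone deviations, and do not count omissions that the protocol itself requires.

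The cost is one corrected sentence, with no added patients, visits, procedures or analyses. Section 14.1 reports that 27 patients have already been accrued but not where they are in treatment. If maintenance is complete, the remaining value of the correction lies in classifying deviations consistently.
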